3.1.2. Laboratory Safety Tests

Safety laboratory tests will be performed as described in the protocol. In addition, total globulin will be derived as total protein(g/L)-albumin(g/L).

To determine if there are any clinically significant laboratory abnormalities, the hematological, clinical chemistry (serum) and urinalysis safety tests will be assessed against the criteria specified in the sponsor reporting standards. Laboratory parameters identified in [Appendix 2](#) will also be assessed against criteria specified in that appendix. The respective assessments will take into account whether each subject's baseline test result is within or outside the laboratory reference range for the particular laboratory parameter.

Baseline will be the last pre-dose measurement.

3.1.3. Vital Signs

Single supine blood pressure and heart rate measurements will be taken at times detailed in the Schedule of Activities given in the protocol.

Baseline will be defined as the last pre-dose recording.

3.1.4. ECG

A single 12-lead ECG will be obtained on all subjects at screening. If ECG is abnormal, collect triplicate ECG. 12-lead ECGs will be recorded in triplicate for subjects on Day 1. On subsequent days, a single 12-lead ECG will be obtained on all subjects. If ECG is abnormal, collect triplicate ECG.

The QT interval, QTcF interval, PR interval, RR interval, QRS complex and heart rate will be recorded at each assessment time.

If not supplied, QTcF interval will be derived using Fridericia's heart rate correction formula: $QTcF = QT / (RR)^{1/3}$ where $RR = 60/HR$ (if not provided)

The average of the triplicate readings will be calculated for each ECG parameter.

Baseline will be defined as the average of triplicate ECG measurements collected prior to dosing on Day 1.

3.1.5. Injection and Infusion Site Reactions

Injection and infusion site reactions will be monitored for each subject from Day 1 to Day 113.

3.1.6. Other Safety Data

Additional safety data will be collected as described in the protocol and will be listed if collected in the sponsor's database.

3.2. Secondary Endpoints

3.2.1. Efficacy

- *Annualized rate of bleeding episodes; Day 1 up to Day 85.*

Baseline will be defined as the annualized bleeding rate during the 6 months prior to study enrollment.

3.2.2. Pharmacokinetics

- *Plasma PF-06741086 concentrations (Day 1 up to Day 113) and noncompartmental parameters will be calculated as determined by a validated assay:*
 - *Single-dose*
 - *Day 1 to Day 7 (QW): C_{max} , T_{max} , AUC_{last} , C_{168h}*
 - *Day 1 to Day 28 (QM): C_{max} , T_{max} , AUC_{last} , C_{672h} .*
 - *Multiple-dose Day 29 to Day 36 (QW) or Day 29 to Day 57 (QM) $C_{max,ss}$, $T_{max,ss}$, AUC_{τ} , V_{ss} (for IV administration only), CL (for IV administration only) or CL/F (for SC administration only), and C_{min} .*

3.2.3. Pharmacodynamics

- *Total TFPI; Day 1 up to Day 113.*
- *Thrombin generation (including lag time, peak thrombin generation and endogenous thrombin generation potential); Day 1 up to Day 113.*
- *Prothrombin fragment 1+2 (PF1+2); Day 1 up to Day 113.*
- *D-dimer; Day 1 up to Day 113.*
- *Dilute prothrombin time (dPT); Day 1 up to Day 113.*

Baseline will be defined as the last measurement prior to dosing on Day 1.

3.2.4. Immunogenicity

- *Frequency of anti-drug antibody (ADA) and neutralizing antibody (NAb) production against PF-06741086; Day 1 up to Day 113. Only positive ADA samples and the corresponding baseline sample will be tested in the NAb assay.*

Formation of ADA and NAb will be monitored for each subject. Subjects with positive ADA or NAb may be required to attend additional, unscheduled follow-up visits after Day 113. Extended follow up visits every 2 weeks for up to 3 months, including vital signs, immunogenicity, AE and concomitant medication assessments, may be performed.

CCI

3.4. Baseline Variables

Demographics, medical history, hemophilia history, including inhibitor status, target joint and hemophilic arthropathy and bleeding episodes over past 6 months, will be collected at screening visit.

4. ANALYSIS SETS

4.1. Full Analysis Set

In general, the full analysis set is comprised of all enrolled subjects. This population of subjects is not applicable for this study. Analysis sets for efficacy, PK, pharmacodynamic and safety data are defined in [Section 4.3](#), [Section 4.4](#), [Section 4.5](#) and [Section 4.2](#).

4.2. Safety Analysis Set

All subjects who receive at least 1 dose of study medication will be included in the safety analyses and listings.

4.3. Per Protocol Analysis Set

The Per Protocol Analysis Set (PPAS) will be a subset of the Safety Analysis Set. This set will exclude subjects with major protocol deviations.

Major protocol deviations include but not limited to:

- Lack of compliance in study drug administration;
- Violations on concomitant medications, see Protocol Section 5.7.1.

The full list of protocol deviations will be reviewed prior to database lock and a decision will be taken regarding exclusion from the PPAS.

4.4. Pharmacokinetic Analysis Set

Subjects who experience events that may affect their PK profile may be excluded from the PK analysis. At the discretion of the Clinical Pharmacologist, a concentration value may also be excluded if the deviation in sampling time is of sufficient concern or if the concentration is anomalous for any other reason.

4.4.1. Concentration Analysis Set

The PK concentration population is defined as all enrolled subjects treated who have at least 1 quantifiable concentration.

4.4.2. PK Parameter Analysis Set

The PK parameter analysis population is defined as all enrolled subjects treated who have at least 1 of the PK parameters (detailed in [Section 3.2.2](#)).

4.5. Pharmacodynamic Analysis Set

The pharmacodynamic analysis population is defined as all enrolled subjects who receive at least 1 dose of study medication and have a baseline measurement and at least 1 post-dose measurement for at least 1 PD endpoint (detailed in [Section 3.2.3](#)).

4.6. Other Analysis Sets

None.

4.7. Treatment Misallocations

All analyses will be performed on an “as-treated” basis and will not include data from subjects who are enrolled but not treated.

If a subject takes a treatment that is not consistent with the treatment they are assigned to, for example takes a treatment out of cohort, then they will be reported under the treatment that they actually receive for all efficacy, safety, PK and pharmacodynamic analyses, where applicable.

4.8. Protocol Deviations

A full list of protocol deviations will be compiled and reviewed to identify major and minor deviations prior to database closure. Subjects with major protocol deviations may be excluded from an analysis population, as appropriate.

4.8.1. Deviations Assessed Prior to Treatment Assignment

At screening, the investigator will assess subjects against the inclusion and exclusion criteria as set out in Sections 4.1 and 4.2 of the protocol.

4.8.2. Deviations Assessed Post-Treatment Assignment

Any significant deviation from the protocol will be reviewed prior to database closure and a decision taken regarding evaluation for each analysis population.

5. GENERAL METHODOLOGY AND CONVENTIONS

The final analysis will be performed at study subject data set release after LSLV.

5.1. Hypotheses and Decision Rules

Prophylactic treatment with PF-06741086 will be considered superior to On Demand treatment with respect to ABR reduction if 1) the upper limit of the 2-sided 80%CI of the ratio of ABR in PF/historical On Demand is <1 and 2) the estimate of the ratio of ABR in PF/historical On Demand ≤ 0.3 . Drug will be considered not superior to On Demand treatment if the lower limit of the 2-sided 80%CI of the ratio of PF/historical On Demand >0.3 .

The primary efficacy endpoint in the four dose cohorts will be tested in a hierarchical order to control the overall family-wise error rate. The efficacy test will first be performed in the dose cohort with the highest PK exposure (eg, C_{trough} and/or AUC) that is proven to be safe and tolerated. If the result is significant, the ABR will be tested against the historical On Demand group in the dose cohort with the next highest PK exposure. The test procedure will continue until the dose cohort with the lowest PK exposure is tested against the historical On Demand group.

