5.2.3. Analyses for Count Data

Separate models will be run for each pairwise comparison between the historical control group and each dose cohort. The frequency of bleedings will be analyzed using a negative binomial model. Log transformed duration of time on study will be included as an offset variable in the model.

Sample SAS codes are provided as follows:

```
PROC GENMOND Data=sample;
  Where dose='300mg SC';
  Class trt;
  Model count=trt/dist=negbin link=log offset=logtime alpha=0.2 ;
  Estimate 'PF-06741086 - PCB' trt 1 -1;
  Estimate 'PF-06741086' intercept 1 trt 1/alpha=0.2;
  ods output ParameterEstimates=pvalue estimates=est;
```

Run;

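### A cohort with zero bleeds has no usable upper limit for the SAP 5.1 superiority rule, so it ends inconclusive and testing of any lower-exposure cohort stops

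*SAP*

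**What the plan says.** SAP 5.1 sets two conditions for superiority: that "the upper limit of the 2-sided 80%CI of the ratio of ABR in PF/historical On Demand is <1", and that "the estimate of the ratio of ABR in PF/historical On Demand" is at most 0.3. It gives a separate rule for the opposite conclusion: "Drug will be considered not superior to On Demand treatment if the lower limit of the 2-sided 80%CI" of the ratio is above 0.3. Results between the two rules have no label.

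The cohorts are tested in order of falling exposure. SAP 5.1 states: "If the result is significant, the ABR will be tested against the historical On Demand group in the dose cohort" that comes next in that order.

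The model is in SAP 5.2.3: "The frequency of bleedings will be analyzed using a negative binomial model", and "Separate models will be run for each pairwise comparison between the historical control group and each dose cohort". The sample code has the line "Model count=trt/dist=negbin link=log offset=logtime alpha=0.2" and stores its results with "ods output ParameterEstimates=pvalue estimates=est". SAP 6.2.1.1 takes the ratio, its 80% interval and the p-value from this model. No section says what to do with a cohort that has no bleeds. SAP 5.3.4 covers only missing data.

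**The concern.** The rule needs a finite upper limit. A log-link model fitted by maximum likelihood cannot supply a Wald limit for a group with no events, because the fitted rate runs towards zero. Each cohort is fitted alone against the controls, so it cannot borrow events from other cohorts.

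The rule would therefore be non-monotone: it accepts a cohort with one bleed and withholds superiority from a cohort with none. Testing starts at the highest exposure. If bleeding falls with exposure, that is where a zero count is most likely and where a stop leaves the most cohorts untested.

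**Working it through.** **Inputs.** From Protocol 9.1: control rate 2.36 bleeds per patient-month, 6 subjects per cohort, 85% reduction, one-sided alpha 0.1 (z = 1.2816, the same as a two-sided 80% interval), 3 months. From SAP 3.2.1: bleeds are counted from Day 1 to Day 85, that is 84 days or 84/365.25 × 12 = 2.760 months. Assumed, because the documents do not give them: negative binomial dispersion k from 0 (Poisson) to 2, and the size of the control group.

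**The plan's own figure.** Protocol 9.1 states more than 80% power. Expected bleeds over 3 months are 6 × 7.08 × 0.15 = 6.372 on treatment and, with 6 controls, 42.48 in the control group. SE = √(1/6.372 + 1/42.48) = 0.425. Power = Φ(1.897/0.425 − 1.2816) = 99.9%. With the control rate known it is 99.98%. The stated bound is met.

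**Zero bleeds under Wald limits.** With fitted mean μ per treated subject and μ₀ per control, the upper log limit is ln(μ/μ₀) + 1.2816 × √((1/μ + k)/6 + control term). As μ goes to 0, the first part falls like ln μ but the second grows like μ^(−1/2), so the limit is unbounded. Fits to simulated controls (24, 50 or 100 controls, k = 0.5 or 1) behaved this way:
- Maximum likelihood stopped at log ratios of −20.6 to −38.9, with SE from 4,900 to 45 million.
- Under Fisher scoring the upper ratio was above 1 by iteration 8 and had overflowed by iteration 25.
- The Wald p-value is equally uninformative: −20.6/4,900 = −0.004.

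The printed value depends on when the software stops. A fit halted at about 5 iterations would show a spurious limit below 1.

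**One bleed.** At the control rate, 6 subjects would have 6 × 2.36 × 2.760 = 39.08 bleeds. The ratio is 1/39.08 = 0.0256. With the control rate known, SE = √(1 + k/6). The upper limit is 0.0256 × exp(1.2816 × 1) = 0.092 at k = 0, and 0.0256 × exp(1.2816 × 1.155) = 0.112 at k = 2. Both conditions are met.

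**Chance of a zero-bleed cohort of 6.** The mean per subject is m = 6.513 × (1 − reduction). P = exp(−6m) for Poisson and (1 + km)^(−6/k) otherwise. The last column is 1 − (1 − P)³, if the first three cohorts share the same effect.

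| Reduction | m | P per cohort, k = 0 to 2 | At least one of the first three |
|---|---|---|---|
| 85% (planned) | 0.977 | 0.3% to 3.9% | 0.9% to 11% |
| 90% (illustrative) | 0.651 | 2.0% to 8.2% | 6% to 23% |
| 95% (illustrative) | 0.326 | 14% to 22% | 37% to 53% |

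Efficacy is analysed in the per-protocol set, so a cohort may have fewer than 6. With 4 subjects at 85%: exp(−4 × 0.977) = 2.0%, up to (1 + 2 × 0.977)^(−2) = 11.5%.

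**Bounds that do exist (control rate treated as known).** The exact one-sided 90% bound solves P(zero bleeds) = 0.10.
- Poisson: 2.303/39.08 = 0.059.
- k = 2: mean (10^(1/3) − 1)/2 = 0.577 per subject, and 0.577/6.513 = 0.089.

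The 80% profile-likelihood limit allows a log-likelihood drop of 1.2816²/2 = 0.821.
- Poisson: 0.821/39.08 = 0.021.
- k = 2: (exp(2 × 0.821/6) − 1)/(2 × 6.513) = 0.024.

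At the profile limit the chance of zero bleeds is exp(−0.821) = 0.44, not 0.10.

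**The case against.** The SAP never names Wald limits. It asks for an 80% interval and offers the code as a sample, so a programmer could choose another method. This stands as a caveat. But nothing in the text asks for another method, and a choice made after a zero count is seen would be post hoc.

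The practical effect is limited. Safety is the primary endpoint, the Protocol Summary plans no formal hypothesis test, and cohort progression under Protocol 3.3 rests on sponsor review of the data, not on SAP 5.1. ABR is described for every cohort, and the exact Wilcoxon test in SAP 6.2.1.3 handles zeros. All of this holds. Still, the Wilcoxon test is labelled a sensitivity analysis and does not feed the 5.1 rule, and pooling of doses in SAP 6.2.1.2 is optional and depends on a biomarker plateau. Having set a superiority rule with family-wise error control, the SAP needs that rule to return an answer.

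Two stronger readings are tempting, and the documents support neither. A reader might infer that the rule declares an excellent drug not superior. It does not: that conclusion needs a lower limit above 0.3, and the lower limit here is 0. The verdict is missing, not reversed. A reader might also infer that any zero-bleed cohort blocks all the others. It blocks only cohorts later in the order, and in last place it blocks nothing. That is why the table counts three cohorts and not four.

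**Conclusion.** The gap is real and worth closing before database lock. Under the rule and code as written, a zero-bleed cohort cannot meet the first superiority condition, while a one-bleed cohort passes with an upper limit of roughly 0.1. The consequence is an inconclusive result for that cohort and no test of any lower-exposure cohort.

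At the planned 85% reduction the event is uncommon. It becomes likely only if the true effect is well beyond the planned one, and the 90% and 95% reductions are not in the documents. The conclusion rests on reading the limits as Wald limits. Its size rests on 6 subjects followed for 84 days, the protocol's control rate and an assumed dispersion of 0 to 2. The three-cohort figures also assume the same effect in every cohort.

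**What to change.** Add to SAP 5.1 and 5.2.3: for a cohort with zero bleeds, the ratio is taken as 0 and the first condition is judged on an exact one-sided 90% upper bound. State which control rate and dispersion enter the bound. The worked values of about 0.06 (Poisson) and 0.09 (k = 2) treat the control rate as known and so ignore its sampling error, but they lie more than tenfold below 1. The cohort would pass both conditions and testing would continue.

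The profile-likelihood limit (about 0.02) should not be the primary limit, because at zero events it is too small by a factor of 2.8 (0.059/0.021) to 3.7 (0.089/0.024). Limits for cohorts with bleeds stay as planned.

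The cost is one sentence, a few lines of code, and a different interval method for zero-bleed cohorts only.

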### **9.1. Sample Size Determination**

The total sample size of approximately 24 subjects for 4 dose cohorts is based on clinical considerations to provide adequate safety, tolerability, PK, PD and efficacy information at each dose level and/or route of administration. Each single dose cohort includes 6 subjects to ensure sufficient sample size for assessment of safety, PK, PD and efficacy. Additional subjects and/or cohorts may be added to fully explore the dose range and efficacy.

This sample size is also considered sufficient to support initial analyses for efficacy based on the endpoint of annualized bleeding rate (ABR). With 6 subjects per cohort, there is greater than 80% power to detect an 85% reduction in ABR compared to a historical factor-replacement treatment (control group) at one-sided alpha of 0.1. The power calculation is based on a Poisson regression model with assumptions that the historical control group has a bleeding rate of 2.36/patient-month and the study duration is 3 months.

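### SAP 5.1 uses the label 'not superior to On Demand' for a missed 70% target, even when the whole 80% interval lies below 1

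*SAP*

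**What the plan says.** SAP 5.1 sets two verdicts for each dose cohort against the historical On Demand group.

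- **Superior** needs both "the upper limit of the 2-sided 80%CI of the ratio of ABR in PF/historical On Demand is <1" and "the estimate of the ratio of ABR in PF/historical On Demand ≤ 0.3".
- The opposite verdict has one condition: "Drug will be considered not superior to On Demand treatment if the lower limit of the 2-sided 80%CI" of that ratio is above 0.3. Nothing is required of the upper limit.

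Results that meet neither rule get no label, and the SAP gives no reason for choosing 0.3. The same section tests the cohorts in order of exposure and moves on when a result is significant, without saying whether that means the upper limit alone or both conditions. SAP 6.2.1.1 requires the ratio, its 80% interval and a p-value for each cohort. The Wilcoxon sensitivity analysis (SAP 6.2.1.3) uses a one-sided p below 0.1, has no 0.3 threshold, and follows the same hierarchy.

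**The concern.** Two questions are merged under one word. Whether the drug does better than on-demand treatment is a question about a ratio of 1. Whether it reaches a 70% reduction is a question about a ratio of 0.3. The negative verdict is triggered only by the second question but is worded as an answer to the first.

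A cohort with an interval of 0.35 to 0.75 would be recorded as not superior to on-demand treatment although its interval excludes 1. The same cohort could be statistically significant in the Wilcoxon analysis. Efficacy is the key secondary objective, and a reader who sees only the verdict would take it to mean that no benefit over on-demand treatment was shown.

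**Working it through.** **Inputs from the documents.** Protocol 9.1: 6 subjects per cohort; "the historical control group has a bleeding rate of 2.36/patient-month and the study duration is 3 months"; one-sided alpha 0.1, which matches the limits of a two-sided 80% interval (z = 1.2816). Expected bleeds per control subject over 3 months: 2.36 × 3 = 7.08. SAP 5.2.3: negative binomial model with a log-time offset.

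**Assumed, because the documents do not give them.** Size and follow-up of the control group, and the negative binomial dispersion k. Ranges are shown below.

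**1. The plan's own power figure.** Protocol 9.1 states: "With 6 subjects per cohort, there is greater than 80% power to detect an 85% reduction in ABR". With a Poisson model and 6 controls followed for 3 months:

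SE of log ratio = sqrt(1/(6 × 7.08 × 0.15) + 1/(6 × 7.08)) = sqrt(0.1569 + 0.0235) = 0.425

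Power = Φ(1.897/0.425 − 1.2816) = 99.9%. The stated figure is satisfied.

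**2. When the two conditions overlap.** The lower limit exceeds 0.3 if the estimate is above 0.3 × exp(1.2816 × SE). The upper limit is below 1 if the estimate is below exp(−1.2816 × SE). Both can hold only if

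SE < −ln(0.3)/(2 × 1.2816) = 1.204/2.563 = 0.470.

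**3. A worked case.** Take 21 bleeds in 6 subjects over 3 months. Ratio = (21/6)/7.08 = 0.494. Control counts are set at their expected value, and SE² = 1/21 + 1/(7.08 × nc) + k/6 + k/nc, where nc is the number of controls.

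| Assumption | SE | 80% interval | One-sided p | Verdict in SAP 5.1 |
|---|---|---|---|---|
| Poisson, 6 controls | 0.267 | 0.35 to 0.70 | 0.004 | not superior |
| k = 0.25, 50 controls | 0.312 | 0.33 to 0.74 | 0.012 | not superior |
| k = 0.5, 6 controls | 0.488 | 0.26 to 0.92 | 0.074 | none |

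All three intervals exclude 1. Two get the negative label and the third gets no label.

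**4. How often it occurs.** Chance of a lower limit above 0.3 together with an upper limit below 1, from simulation with k treated as known, 30 controls followed for 1 year and a true 50% reduction:

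| k | SE at the expected counts | Chance |
|---|---|---|
| 0.3 | 0.329 | 41% |
| 0.7 | 0.434 | 9% |
| 1.0 | 0.498 | 0% |

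The SE comes from sqrt(1/21.24 + 1/849.6 + k/6 + k/30). A simulation of 800 trials per scenario that estimates k from the data gives 40%, 11% and 2%.

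With control follow-up of 3 months the chance at a true ratio of 0.5 is 64% (Poisson, 6 controls), 77% (Poisson, 50 controls), 19% (k = 0.25, 6 controls), 47% (k = 0.25, 50 controls), 24% (k = 0.5, 50 controls) and about 0% (k = 0.5 with 6 controls, or k = 1). At the design ratio of 0.15 it is about 0.1% or less throughout.

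**5. The unlabelled zone.** An estimate above 0.3 with a lower limit at or below 0.3 and an upper limit below 1 occurs in 24% of trials at a true ratio of 0.5 and 38% at 0.3 (Poisson, 6 controls).

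**The case against.** The strongest reply is that the SAP defines its own term. Superior requires both conditions, and a lower limit above 0.3 forces the estimate above 0.3, so the second condition has already failed. Under that definition 'not superior' is correct, and the two verdicts can never both apply. This stands. A reader might infer that the rule contradicts itself or that the label is simply false; the text of SAP 5.1 does not support that.

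Second, a reader might infer that a proven reduction would be hidden. SAP 6.2.1.1 requires the ratio, interval and p-value for every cohort, so the evidence is shown. 'Proven' would also be too strong: it would rest on an 80% interval from 6 subjects against a non-randomised pool of earlier studies. With such a comparator, asking for more than an upper limit below 1 is a reasonable safeguard. This stands too.

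Third, a reader might infer that superiority should be declared on the upper limit alone. That would remove the 0.3 condition. At a true ratio of 0.5 (30 controls, 1 year) the chance of declaring superiority would rise from 9% to 84% at k = 0.3, and from 20% to 59% at k = 1.0. The documents give no reason to loosen the rule in this way.

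Finally, the Protocol Summary says that no formal hypothesis test is planned. That lowers the stakes, but SAP 5.1 still sets out a decision rule with named verdicts, and the names should say what was tested.

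**Conclusion.** The point holds as a labelling fault. The negative verdict in SAP 5.1 rests only on ruling out a 70% reduction, yet it is worded as a comparison with on-demand treatment and can be given when the whole 80% interval lies below 1. The thresholds themselves are a legitimate go/no-go choice.

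The frequency cannot be fixed from the documents. It matters for moderate true effects with low to moderate dispersion. It is negligible at the effect the trial was sized for, and it disappears once the SE of the log ratio reaches 0.470. Two related gaps need no assumption: the middle zone has no label, and the hierarchy does not define significance.

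**What to change.** Change the wording of SAP 5.1 and leave both thresholds as they are:

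- Upper limit below 1 and estimate at or below 0.3: 'superior with target effect met'.
- Lower limit above 0.3: 'target effect (70% reduction) not met'.
- Everything else: 'inconclusive for the target effect'.
- For every zone, state separately whether the upper limit is below 1, and say that this alone is not the go criterion.
- Say which criterion 'significant' refers to in the hierarchy. The choice decides how far testing proceeds, as the 9% against 84% above shows.

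The relabelling is a text edit. It needs no new data or analysis and does not change the chance of the positive verdict. The downside is that a cohort may be reported as better than on-demand treatment at the 80% level but short of the target, against a non-randomised control. The report should state that limitation beside the result.
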